(c) Oral bacteria will be measured using a GenProbe for Chlamydia trachomatis at delivery or visit 7 (36 weeks). A swab is used to make the oral collection by gently swabbing the inside of the cheeks and oral cavity. The dichotomous outcome for Chlamydia (positive or negative) will be analyzed with respect to the periodontal measures, BOP, and birth outcomes. Trained study personnel will perform the oral bacterial test. Data will be recorded on the visit questionnaire. This research instrument has been previously used in the research environment.

(18) Labor and Delivery Questionnaire: Characteristics of each mother's labor and delivery will be recorded on a data form. Prior complications of pregnancy will be listed on the monthly pregnancy assessment questionnaire. Such complications at the time of delivery will be listed here according to ACOG definitions: e.g., preeclampsia; HELLP syndrome; gestational diabetes; hypertension; preterm labor; premature rupture of membranes (PROM); deep venous thrombosis or a coagulopathy; maternal infection such as varicella or herpes (primary or secondary); placental abnormalities such as previa or abruption. The following information about labor will be included: (a) length of labor, (b) use of pitocin augmentation, (c) time of rupture of membranes, and (d) complications of labor: fetal distress or decelerations, failure to progress, shoulder dystocia, breech presentation or abnormal fetal lie. Should the infant be delivered at an outlying hospital, mother will complete a release of medical information form so that medical records relating to the labor and delivery and the infant's health status/physical examination will be forwarded to the Clinical PI.

(19) Maternal Body Mass Index (BMI) Measurement: Pre-pregnancy height and weight of each mother will be recorded at the first outpatient visit to determine BMI (weight [kg]/height² [m²]). During subsequent outpatient visits, only the mother's weight will be recorded.

(20) Maternal Baseline and Monthly Calcium and C-Reactive Protein Serum Studies: Whole blood (3.5 mL) will be obtained from each mother at the time of her scheduled obstetrical visit monthly as well as at delivery and placed in an SST tube. The blood will be sent to the Clinical Chemistry Laboratory. The following blood studies will be measured: total Ca and C-reactive protein. These results will be reported directly to [name], then entered into the Study's Database.

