(21) Maternal Baseline and Monthly Vitamin D and Calcium Homeostatic Parameters: A 14 mL sample of whole blood will be drawn from the mother at the scheduled obstetrical visit monthly as well as at delivery and placed in an SST tube to be processed in the CTRC Clinical Laboratory for serum separation. The serum will be placed in a -80°C freezer and sent to [name] laboratory on dry ice. Each serum sample will be analyzed for maternal circulating levels of total 25(OH)D, 1,25(OH)₂D, iPTH (5), batched for serum cytokine analysis, and batched for measurement of megalin and cubulin. 25(OH)D will be run on all subjects after 3 months supplementation. Mothers who are still frankly vitamin D deficient (less than 15 ng/ml) will be placed on open label vitamin D gummies for the remainder of their pregnancy.

(22) Monthly Maternal Urine Sample: A random urine sample will be obtained from the mother at each obstetrical visit to be sent to the Clinical Chemistry Laboratory for urinary Ca and creatinine measurement and derivation of the urinary Ca: creatinine ratio. This ratio will be used as an indicator of hypercalciuria that precedes hypercalcemia. Results of these urine studies will be reported directly to [name]. An additional aliquot of the urine sample will be frozen for future cytokine analysis.

(23) Cord Blood Vitamin D and Calcium Measurements. At the time of delivery, 10-mL of whole blood will be drawn from the umbilical vein then sent to the CTRC Clinical Laboratory facility for processing. One red bullet (0.5 cc aliquot) will be sent to the Clinical Chemistry laboratory for measurement of total calcium and creatinine. The remaining blood will be processed in the CTRC Clinical Laboratory immediately for serum separation and placed in a -80° C freezer then transported on dry ice to [name] laboratory for later determination of each neonate's circulating levels (at the time of delivery) of intact iPTH, total 25(OH)D, and 1,25(OH)₂D (5). Additional frozen serum will be batched for analysis of cytokines. Every effort will be made to collect cord blood at the time of delivery. An additional 15 mL plasma sample will be obtained from the cord for immune privilege flow cytometry studies.

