Potential Risks of Vitamin D Supplementation: There is a possibility that the treatment (dose of vitamin D) that each subject receives may prove to be less effective or to have more side-effects than the other study treatment (other dose of vitamin D) or other available treatments. The risks of maternal high dose vitamin D supplementation are hypercalciuria and hypercalcemia. There is a small risk that the woman's blood calcium level would increase in response to higher dose vitamin D supplementation. In the more than 540 women in the two prior vitamin D pregnancy supplementation trials (5, 6) and in the more than 340 mothers and infants who participated in the recently completed vitamin D lactation supplementation trial conducted at MUSC and the University of Rochester, this has not happened previously at this dose. The dose of vitamin D (4400 IU/day) used in this study is just over the limits established by the Institute of Medicine in 2010 (3). The PI and co-investigator do have an IND from the FDA (IND 66,346) for the administration of this dose of vitamin D and a higher dose in pregnant and lactating women; this protocol has been added to the IND. If, after 3 months on vitamin D supplementation, a woman is still frankly vitamin D deficient (less than 15 ng/ml), she will receive open label vitamin D gummies as requested by the FDA (IND 66,346). In two previous large randomized controlled trials of vitamin D supplementation during pregnancy and one large randomized controlled trial of vitamin D

supplementation during lactation, there was no difference in serum calcium or urinary calcium/creatinine ratios between the treatment groups (please see attached papers).

Potential Risks to the Fetus: During pregnancy, the developing fetus' vitamin D levels are about 70% of maternal serum vitamin D levels (5, 6). In the more than 540 women who participated in our two previous vitamin D supplementation studies, there was no identified increased risk to the developing fetus as per our two Data Safety and Monitoring Committees. Yet, some unknown risk of high dose maternal vitamin D supplementation on the fetus could be possible. By monthly monitoring of maternal serum vitamin D levels, we will ensure that the fetal levels remain in the normal range.

Potential Risks of Vaginal Swabs: Vaginal swabs obtained by the subjects do not carry a risk greater than insertion of a tampon.

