The second statistical approach measures the effects of the confounders and takes the more traditional approach of assuming normal distribution for Vitamin D, and will be performed in parallel fashion to compare treatment effects in 400 IU and 4400 IU vitamin D groups. The primary research aim is to determine if supplementation is associated with an increase in vitamin D concentrations. As discussed below, it will be necessary to identify and control for other factors (confounders) that may also be associated with changes in vitamin D levels.

Paired analyses according to the study plan will be conducted by employing McNemar chisquare for categorical variables, paired t-tests for normally distributed variables, repeated measures ANOVA for longitudinal analyses, and multiple linear regression for multi-variable analyses to control for confounding. Correlation will be used to assess the linear association between outcomes and those factors expected of an accumulated dose-response relationship (e.g., sunlight exposure), and individual regression tests to identify the strength of the association between outcomes and each characteristic. The resulting coefficients then will be translated into a formula for the linear association between each factor and outcomes. In the event that there are non-linear distributions, appropriate data transformations will occur as necessary.

Both groups will be compared for differences in any factors at baseline, and will include: information contained in the maternal sociodemographic, maternal pregnancy and delivery, and maternal calcium, creatinine, vitamin D₃, 25(OH)D, and urinary calcium creatinine ratio. While the stratified blocked randomization technique should minimize the potential for baseline differences, this first step will confirm whether there should be adjustment for any initial differences in follow-up analyses. Next, differences between baseline and follow-up will be examined for those variables that may have changed over the follow-up period (health assessment; physical activity; and blood and urine outcome measures) to identify those factors that may serve as confounders or effect modifiers for the vitamin D assessments. The potential influence of identified confounders or interaction terms will have to be considered for any change in vitamin D status.

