Changes in vitamin D outcomes will be compared between treatment arms with the additional information from sunlight exposure, pigmentation/melanin index, maternal physical activity assessment, maternal dietary history, health, and medication questionnaires. This detail will allow the separation of changes in vitamin D parameters as a function of confounding factors from supplementation. The study is powered to explore the degree to which changes in vitamin D parameters are a function of supplementation and ethnicity. To assess whether there are differences in the slopes or linear dissimilarities in the outcomes over time, repeated measures techniques will be used to compare longitudinal changes in outcomes between groups. This technique also provides a graphical depiction of the slopes over time and can identify if there are linear or plateau responses to differences in vitamin D supplementation concentration; it also will allow determination of data transformation techniques required for subsequent analyses if the slopes over time are non-linear.

The final step in the second statistical approach will determine whether potential group differences in the various outcomes are a function of any of the potential confounders—with particular attention to skin pigmentation and sunlight exposure. This step will identify changes in outcomes associated with population factors independent of the group (supplementation) assignment. The extent of more complex statistical analyses will be predicated on the number of individuals comprising specific strata, and thus, restricted by a reduction in the statistical power. Such comparisons will be reported as information for future studies. To clarify, using sunlight exposure as a representative example, the independent effect of vitamin D supplementation may be found to have been modified by the amount of sunlight exposure. As such, the changes in outcomes attributable to each factor, independently, and then when considered in combination will be partitioned. While the major goal of this study is to examine the various outcomes as an independent function of vitamin D supplementation—thereby controlling for all other group differences, the changes in outcomes that are associated with these group differences will be examined and reported in detail. In this way, the changes in vitamin D that are associated with each factor independently will be partitioned.

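### The SAP's second approach may adjust the 25(OH)D arm comparison for follow-up laboratory measures that the dose itself can change (minor)

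*SAP*

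**What the plan says.** The primary analysis (SAP, opening paragraphs) is an intention-to-treat comparison of maternal 25(OH)D by Mantel-Haenszel mean scores, weighted across ethnicity. It uses no follow-up covariates.

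A second approach runs in parallel and assumes normality. It holds that "it will be necessary to identify and control for other factors (confounders) that may also be associated with changes in vitamin D levels", and it names multiple linear regression as the tool. After a baseline comparison of the arms, it looks at changes from baseline to follow-up. Besides questionnaire data on health and activity, this step takes in "blood and urine outcome measures) to identify those factors that may serve as confounders or effect modifiers for the vitamin D assessments". Whatever it finds must then have its influence weighed for any change in vitamin D status.

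The next paragraph compares the arms using "additional information from sunlight exposure, pigmentation/melanin index, maternal physical activity assessment, maternal dietary history, health, and medication questionnaires". No laboratory measure is on that list. The same paragraph says that "repeated measures techniques will be used to compare longitudinal changes in outcomes between groups".

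The Protocol shows which follow-up measures could be meant:

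- **D(20), monthly blood:** "The following blood studies will be measured: total Ca and C-reactive protein".
- **D(21), monthly blood:** 25(OH)D, 1,25(OH)2D and iPTH, with cytokines, megalin and cubilin batched.
- **D(22), monthly urine:** calcium, creatinine and their ratio. On the ratio the Protocol says: "This ratio will be used as an indicator of hypercalciuria that precedes hypercalcemia".

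Under potential risks (section E.1) it states: "The risks of maternal high dose vitamin D supplementation are hypercalciuria and hypercalcemia".

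**The concern.** A confounder of a randomised comparison must precede treatment, or at least lie beyond its reach. Follow-up calcium, the urinary ratio, 1,25(OH)2D and iPTH do neither. The Protocol names raised calcium in blood and urine as risks of the dose. Section B describes 25(OH)D as the substrate for 1,25(OH)2D, which in turn regulates parathyroid hormone. These measures are therefore possible consequences of treatment or of the outcome.

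The SAP has no rule that keeps such variables out. Its screen looks for change after baseline and association with vitamin D, and a measure that responds to 25(OH)D is well placed to show both. If one were then entered as a covariate, the model would remove part of the supplementation effect that it is meant to estimate. Using such a measure as an effect modifier has a similar defect, because it groups women by something that treatment may have altered.

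What is at stake is the second-approach estimate of the dose effect on 25(OH)D, and how far it can be compared with the primary estimate.

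**Working it through.** The plan gives no figure on this point, so there is none to reproduce. The check has two parts.

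**1. Which variables the screen admits.** D(22) schedules only calcium, creatinine and their ratio as urine results (a further aliquot is frozen for later cytokine work). The urinary ratio must therefore fall within the screen. Calcium, 1,25(OH)2D and iPTH fall within it on a plain reading of blood outcome measures, although that step names none of them.

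**2. What adjustment would do.** Let T be the arm (0 or 1), Y be 25(OH)D and M a follow-up measure that responds to dose only through Y.

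- Y = δT + e, with var(e) = σ²
- M = bY + u, with var(u) = τ²
- Within-arm squared correlation of Y and M: r² = b²σ² / (b²σ² + τ²)
- Coefficient of M in the regression of Y on T and M: γ = bσ² / (b²σ² + τ²)
- Coefficient of T: δ − γbδ = δ(1 − r²)

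The arm difference therefore shrinks by the proportion r². The sign of r does not matter, so the result applies equally to iPTH, which would be expected to fall.

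Inputs for an illustration:

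- σ = 13 ng/mL, rounded from the SDs of change of 13.2 and 12.9 in the earlier community health center trial (Protocol, section C)
- 150 completers per arm, which is half of the 300 in Protocol E.1
- δ = 15 ng/mL (assumed)
- r from 0.1 to 0.5 (assumed)

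| r | Shrinkage r² | 15 × (1 − r²), ng/mL | Loss, ng/mL | Simulated estimate (200,000 women), ng/mL |
|---|---|---|---|---|
| 0.1 | 1% | 14.85 | 0.15 | 14.84 |
| 0.2 | 4% | 14.40 | 0.60 | 14.49 |
| 0.3 | 9% | 13.65 | 1.35 | 13.67 |
| 0.5 | 25% | 11.25 | 3.75 | 11.27 |

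The standard error of the unadjusted difference is 13 × √(2/150) = 1.50 ng/mL. A loss of 1.35 is 0.9 standard errors and a loss of 3.75 is 2.5. At r = 0.5 the remaining 11.25 is still 7.5 of those standard errors from zero. The estimate would be too small, but the conclusion that the dose raises 25(OH)D would survive.

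**The case against.** The strongest reply is that the harm is conditional at every step. The SAP speaks of factors that may act as confounders and says that their influence must be considered. It does not say that each one enters the model. The list actually used to compare arms has no laboratory measure, and the final step stresses skin pigmentation and sunlight. For calcium and the urinary ratio, the Protocol also reports of the earlier trials that "there was no difference in serum calcium or urinary calcium/creatinine ratios between the treatment groups". That suggests a weak response and so a small r. All of this stands, and it is why the point is minor.

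The reply does not remove the point. The screening sentence still names these measures as candidates and nothing excludes them. The reassurance from earlier trials covers the two calcium measures only. It does not extend to 1,25(OH)2D or iPTH, which the Protocol's own physiology ties more closely to 25(OH)D.

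Three stronger readings are tempting, and the documents support none of them:

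- **That the SAP requires adjustment for calcium or other laboratory results.** It permits this; it does not prescribe it.
- **That the trial's main result is at risk.** The SAP rests the primary analysis on Mantel-Haenszel mean scores, which take no follow-up covariates.
- **That hypercalcemia and hypercalciuria go unanalysed because no final rate by arm is specified.** Out-of-range values go to the monitoring committee with source documents (Protocol E.5.B), interim safety analyses are provided for (E.5.C), and the SAP's repeated-measures comparison of outcomes may already give means by arm. Analysts could tabulate rates by arm without changing the plan. This is detail left unstated, not an error.

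**Conclusion.** The concern holds as a minor point about the second approach only. The screen is worded so that post-randomisation, dose-responsive laboratory measures can become adjusters of the 25(OH)D arm comparison. If one did, the estimated difference would be too small by about r squared: 1-9% at r = 0.1-0.3 and 25% at r = 0.5.

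The size rests on two assumptions. The first is the value of r, which neither document gives. The second is that the measure responds to dose only through 25(OH)D. If it also responded by another route, or shared unmeasured causes with 25(OH)D, the bias would not follow this formula. Lower values of r seem more likely for calcium and the urinary ratio. Higher values are more plausible for 1,25(OH)2D and iPTH.

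**What to change.** Replace the screening sentence in the SAP's second approach with a rule in three parts:

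1. The confounder and effect-modifier screen, and any adjustment of the 25(OH)D arm comparison, use only baseline values (including baseline 25(OH)D, calcium and calcium:creatinine) and factors that the dose cannot change, such as season, sunlight exposure and pigmentation.
2. All post-baseline blood and urine laboratory measures are excluded as adjusters. This covers calcium, the urinary ratio, 1,25(OH)2D and iPTH.
3. Those measures are analysed only as outcomes, by randomised arm.

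The cost is one paragraph, with no new samples, visits or staff and no change to the primary analysis or to safety monitoring. The association of follow-up calcium or iPTH with 25(OH)D can still be described within arms, provided that it is kept apart from the estimate of the treatment effect.

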Preventing Health Disparities during Pregnancy through Vitamin D Supplementation

NCT#01932788

11/6/2013

Statistical Analysis: The primary analysis in this investigation will compare levels of maternal 25(OH)D across the two supplementation groups as 'Intention-to-Treat' and will employ Mantel-Haenszel mean scores; however, a 'Per Protocol' (oversampling to consider attrition) analysis also will be done. This two-step analysis provides information regarding the efficacy of these dosage levels in increasing vitamin D and the effectiveness of oral supplementation to increase vitamin D. Whether the losses are random or are biased with respect to ethnicity, or supplementation arm will be tested. Any differential losses will be reported and examined with the use of propensity scores.

Because of the unique nature of the contributions of potential confounders, two approaches to the analysis will be employed. The first and primary analysis will use a Mantel-Haenszel estimate of the mean treatment difference, computed from stratum-specific treatment differences, which will utilize a weighted average of treatment differences across ethnicity. Mean differences will be calculated for the experimental dosage relative to the 400 IU group. Bonferroni adjustments will be made for the Type I per comparison error rates to correct for multiple testing. The treatment differences, estimated variances, and confidence intervals for the differences will be estimated for maternal serum 25(OH)D. This mode of analysis is quite effective in clinical trials as it is less dependent on normal theory assumptions and associated assumptions such as homogeneity of variance. Parametric models also will be fit, but the primary analysis will rest on Mantel-Haenszel mean scores techniques readily done within SAS. Parametric dose response curves also will be generated to describe the relationship between 25 (OH)D and dosage.

The proportion of participants who completed the daily supplement regimen will be estimated, with a similar "per protocol" style analysis restricted to those individuals. Finally, techniques of multiple linear regression will be employed to describe the interactive effects of ethnicity, as well as the effects of other covariates, such as seasonality, mother's age and fecundity, on baseline serum 25(OH)D. These models will be assessed for violations of the model assumptions, and corrected for such violations as appropriate.

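### The supportive second approach does not limit its arm-effect model to pre-randomisation covariates, so adjusting for a treatment-affected variable could bias that estimate

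*SAP*

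**What the plan says.** The SAP makes the ethnicity-stratified Mantel-Haenszel mean difference primary. The second statistical approach runs in parallel, assumes normality, and also compares the 400 and 4400 IU arms.

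Within that second approach:

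- Its opening paragraph calls it necessary to identify and control for confounders of change in vitamin D level. The next paragraph names "multiple linear regression for multi-variable analyses to control for confounding".
- After a baseline comparison, measurements taken later are screened as well, and the stated purpose is "to identify those factors that may serve as confounders or effect modifiers for the vitamin D assessments". Factors so identified must then be considered for any change in vitamin D status. The SAP spells out what goes into this screen: "health assessment; physical activity; and blood and urine outcome measures".
- The two arms are set against each other on change in vitamin D status using data on sun exposure, skin colour and exercise, together with the "maternal dietary history, health, and medication questionnaires". No time point is given for these readings, and no blood or urine marker is on this list.
- The closing paragraph describes the major goal as the independent effect of supplementation, "thereby controlling for all other group differences".

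The SAP gives no fixed covariate list for the arm-effect model, does not restrict it to pre-randomisation variables, and does not exclude variables that treatment may change.

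**The concern.** In a randomised comparison, a variable that the assigned arm has altered cannot be a confounder of the arm effect. It is a mediator, a consequence of the outcome, or a variable sharing other causes with the outcome. Adjusting for it removes part of the effect or adds bias.

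The protocol makes such variables plausible. Section B places 1,25(OH)2D and parathyroid hormone downstream of 25(OH)D, and section D(21) measures both monthly. Section D(12) collects health and medication data at enrolment and then monthly. Sections A and E.4 expect better vitamin D status to improve maternal health, so the monthly health readings may themselves respond to treatment.

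At stake is the size of the arm effect in the supportive analysis. A shrunken or shifted estimate would stand beside the primary one with no rule for explaining the gap.

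**Working it through.** The plan states no figure on this point, so there is none to reproduce. The size below is an illustration.

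**Inputs**

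- SD of change in 25(OH)D: about 13 ng/mL, from 13.2 and 12.9 in the earlier 2000 vs 4000 IU trial (Protocol C).
- Completers: 300, half per arm, so 150 per arm (Protocol E.1).
- True 400 vs 4400 IU difference d: not given; assumed range 3 to 15 ng/mL. The low end is the 2000 vs 4000 IU contrast, 15.2 − 12.2 = 3.0 (Protocol C). The upper part is more likely here: Protocol B says that 400 IU/day hardly moves 25(OH)D, and Protocol C reports +15.2 on 4000 IU.
- Within-arm correlation r of a marker with 25(OH)D: not given; assumed 0.3 to 0.7.

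**Step 1: general formula.** Let the arm shift a follow-up variable by *a* SDs, and let that variable have within-arm correlation ρ with 25(OH)D. Adding it to the regression changes the arm coefficient by −13·ρ·*a*.

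**Step 2: a marker driven by 25(OH)D.** Here ρ = r and *a* = r·d/13, so the change is −13·r·(r·d/13) = −r²·d and the adjusted effect is d(1 − r²). The sign of the marker's relation to 25(OH)D does not matter.

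| r | Loss (r²) | d = 10: formula (simulated) | d = 15: formula (simulated) |
|---|---|---|---|
| 0.3 | 9% | 9.10 (9.05) | 13.65 (13.69) |
| 0.5 | 25% | 7.50 (7.47) | 11.25 (11.22) |
| 0.7 | 49% | 5.10 (5.05) | 7.65 (7.66) |

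The simulation used 150 per arm, SD 13 and 1,500 runs per cell.

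**Step 3: a health or medication variable sharing other causes with 25(OH)D.** With assumed *a* of 0.1 to 0.3 SD and ρ of 0.1 to 0.5, the bias runs from 13 × 0.1 × 0.1 = 0.13 to 13 × 0.5 × 0.3 = 1.95 ng/mL, in either direction. A covariate that the arm does not affect (*a* = 0) gives none.

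**Step 4: which variables could carry the larger losses?** At d = 15, Step 2 needs the arm to shift the marker by 0.5 × 15/13 = 0.58 SD at r = 0.5, or 0.7 × 15/13 = 0.81 SD at r = 0.7. Protocol E.1 reports no arm difference in serum calcium or urinary calcium/creatinine in three earlier trials. Shifts of that size fit poorly with this, so the risk for the calcium measures is small. No such reassurance is given for 1,25(OH)2D, iPTH or follow-up health status.

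**Step 5: significance.**

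- Unadjusted SE = 13·√(2/150) = 1.50.
- Adjusted SE = 1.50·√[(1 − r²)(1 + (d·r/13)²/4)].
- At d = 15, z is 9.99 unadjusted and 9.39, 8.31 and 6.62 at r = 0.3, 0.5 and 0.7.
- The true difference that gives z = 1.96 is 2.94 unadjusted and 4.15 at r = 0.7. Expected significance at the nominal 5% level is therefore lost only if the true difference lies between 2.94 and at most 4.15 ng/mL.

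**The case against.** The strongest reply is that the SAP never says these follow-up values will enter the arm-effect model. Identified factors are only to be considered. The list for the arm comparison contains no blood or urine marker, and 1,25(OH)2D and iPTH are not named in the SAP and may be meant as outcomes. The final step looks for factors that act independently of assignment, with emphasis on pigmentation and sunlight. More complex comparisons are to be reported as information for future studies. The primary estimate would be shown in any case.

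Much of this stands, and it limits the point. A reader might infer that the plan orders adjustment for downstream markers; the text supports only that it allows it. But the list for the arm comparison does not withdraw the follow-up screen, and it does include health and medication with no time point. Because control of confounders is called necessary, a variable that passed the screen would probably be adjusted for. The emphasis on arm-independent factors is not an exclusion rule.

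A reader might also suspect that delivery data enter the baseline comparison, which covers "information contained in the maternal sociodemographic, maternal pregnancy and delivery, and maternal calcium". The SAP says that these factors are compared at baseline, so earlier obstetric history (Protocol E.1, Sources of Materials) is the natural reading.

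**Conclusion.** The concern holds as a minor one. The second approach screens post-randomisation variables as confounders and does not limit its arm-effect model to pre-randomisation covariates. Following the plan could therefore bias the supportive estimate.

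For a marker driven by 25(OH)D, the loss is 9% to 49% over r = 0.3 to 0.7; r is assumed throughout. For health or medication variables, the bias could be about 0.1 to 2.0 ng/mL either way, also under assumed inputs. For the calcium measures it is probably small.

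Two stronger conclusions are tempting and are not supported. One is that the supportive comparison would lose significance. That needs a true difference of about 3 to 4 ng/mL, which is unlikely for 400 vs 4400 IU given the protocol's own account of both doses. The other is that the main result is compromised. The Mantel-Haenszel analysis stratifies by ethnicity only and uses none of these variables.

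**What to change.** State in the SAP that any second-approach model reporting the arm effect on 25(OH)D adjusts only for covariates measured before randomisation and chosen in advance. Examples are ethnicity, baseline 25(OH)D, maternal age and season at enrolment.

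This would be a new list for this model. The first approach uses ethnicity as the stratifier, and it refers to "the effects of other covariates, such as seasonality" and maternal age only for a regression on baseline 25(OH)D. Baseline 25(OH)D appears in the second approach's baseline comparison.

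Keep the follow-up screen only for effect-modification or mediation analyses labelled exploratory. The sunlight analysis can stay on that footing. If health or medication data are wanted in the arm-effect model, specify the enrolment reading.

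The cost is SAP wording only, with no new data and no change to the primary analysis. The drawbacks are less freedom in choosing covariates after seeing the data, and possibly a little precision lost by not adjusting for follow-up sunlight, diet or activity.
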